5.1.3 Visit 1 (Day 0, in-clinic): Baseline/Randomization/Treatment

The following procedures will be performed:

- Confirm eligibility (review inclusion/exclusion criteria)
- Record concomitant medications
- Conduct pregnancy test, as applicable
- Perform and record physical examination
- Record vital signs (Measure body temperature, SBP, DBP, and pulse rate) pre- and post-injection
- Perform and/or review the final Pre-Baseline WOMAC A pain evaluation using both the 5-point Likert scale and the 100mm VAS scale
- Perform WOMAC B and C prior to treatment
- Perform PGA evaluations prior to treatment
- Randomize patient to study arm
- Perform intra-articular injection of blinded study treatment
- Record post-injection AEs if observed
- Issue rescue medication (acetaminophen [paracetamol])

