10.3.11.3 Concomitant Medications or Treatments

The number and percent of patients receiving concomitant medications or treatments prior to, during the study and at the final visit will be tabulated and presented overall and by treatment group for the ITT analysis population. Concomitant medications/treatments will be summarized using descriptive statistics and will be presented by type of drug (WHO drug classification) overall and by treatment group for the safety and ITT analysis populations.

Treatment failures are defined as patients who receive additional medications or surgical procedures in order to treat worsened symptoms in the treated knee during the study; specifically, treatment failures are any patients who:

- Increase their corticosteroid dose of ≤ 10 mg above their starting dose of corticosteroid during the study to treat worsened symptoms in the treated knee;
- Increase use of NSAID pain medications by a clinically significant amount during the study to treat worsened symptoms in the treated knee;
- Begin opioid treatment during the study to treat worsened symptoms in the treated knee;
- Receive intra-articular injection of pain medicine in the treated knee during the study to treat worsened symptoms in the treated knee;

- Undergo total knee replacement or other surgical procedure in the treated knee prior to assessment of the primary efficacy endpoint.

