10.4.2 Secondary Endpoints

- Change in PGA between Baseline and Week 12
- Change in the 100 mm VAS Pain Scale between Baseline and Week 12
- Use of rescue analgesia (amount of acetaminophen used between Baseline and Week 12)
- Incidence and severity of treatment-emergent adverse events (TEAEs)

A serial gatekeeping approach will be used to test the secondary endpoints in a sequential manner (i.e. PGA, 100 mm VAS, rescue analgesia).

The difference between treatment groups in the mean change in PGA from Baseline to Week 12 will be analyzed using a similar MMRM model, with Treatment assignment, Week, and Baseline value as fixed effects and including patient as a repeated measure with a compound symmetric covariance matrix for residuals.

The difference between treatment groups in the mean change in 100 mm VAS from Baseline to Week 12 will be analyzed using a similar MMRM model, with Treatment assignment, and Baseline value as fixed effects and including patient as a repeated measure with a compound symmetric covariance matrix for residuals.

The difference between treatment groups in the amount of acetaminophen used between Baseline and Week 12 will be analyzed with a Wilcoxon rank-sum test.

All secondary efficacy analyses will be reported with one sided p-values and successively compared to a critical level of 0.025 if each preceding test was significant.

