#### **3.2 Secondary Endpoints**

- Change in PGA between Baseline and Week 12
- Change in 100mm VAS Pain scale between Baseline and Week 12
- Use of rescue analgesia (amount of acetaminophen used between Baseline and Week 12)
- Incidence and severity of treatment-emergent adverse events (TEAEs)

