#### **6.1.3 Per Protocol (PP) Analysis Set**

The per protocol (PP) analysis population is defined as all patients who met all entry criteria and had no major protocol violations. All efficacy analyses will be repeated in the PP population. These analyses will be supportive of the ITT analysis. Patients will be analyzed as treated. No imputations will be performed.

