## **7.2 Handling of Missing and Incomplete Data**

All data collected under this study protocol will be included in the assessment of patient safety. Missing or incomplete AE data will assume greatest relationship to study drug and/or severity. Incomplete adverse event and concomitant medication dates will be imputed as described in Section 12. If imputed dates are used, then they will be identified as such in the final study report. If an AE start date is missing or partially missing and no additional information is available from the site in order to establish whether the event started before or after the dose of study drug, the event will be considered to have started after dose. Partially missing dates where the month and year is prior to Day 0 will be classified as pre-dose.

For the co-primary effectiveness analysis of WOMAC pain change and WOMAC C function change, missing change scores will be imputed when the ITT analysis population is used. Missing data will be imputed by the fully conditional specification predictive mean matching multiple imputation approach of Berglund and Heeringa (2014). A sensitivity analysis will be conducted in which the missing 12-week endpoint is replaced by the Baseline WOMAC pain score.

For the secondary endpoints of PGA, 100mm VAS, and number of acetaminophen pills used, missing values will be imputed when the ITT analysis population is used. Imputation methods employed will be multiple imputation (SAS PROC MI and SAS PROC MIANALYZE) and single imputation methods (i.e., regression-based estimates, Baseline imputation, LOCF, and a worst/best case imputation).

Per the WOMAC User Guide, the patient's response will be regarded as invalid, and the subscale(s) deficient, in the event that two pain, both stiffness, or more than four physical function items are omitted. Further, if one pain, one stiffness, or 1-3 physical function units

are missing, the average value for the subscale will be substituted in lieu of the missing item value(s).

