### 8.6.2 Secondary Effectiveness Endpoints

Secondary effectiveness endpoints will be analyzed using the ITT and the PP analysis populations. All secondary efficacy tests will be performed and reported with one-sided p-values for superiority of Ampion.

Change from Baseline to 2, 4, 6, 8, 10, 12, and 24 weeks for the PGA will be analyzed using a MMRM model. Treatment assignment, Week, and Baseline PGA will be included as fixed effects and a compound symmetric covariance matrix for residuals to reflect the repeated measures.

Change from Baseline to 12 weeks for the 100mm VAS Pain Score will be analyzed using a MMRM model. Treatment assignment, and Baseline PGA will be included as fixed effects and a compound symmetric covariance matrix for residuals to reflect the repeated measures.

Use of rescue analgesia (amount of acetaminophen used) will be compared by treatment arm. A Wilcoxon rank-sum test will be used to compare overall pill count use over the study between saline and Ampion.

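### The gated rescue test counts acetaminophen tablets only, with no rule for counts after treatment failure and two unsuitable imputation methods for missing counts

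*SAP*

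**What the plan says.** **Endpoint.** SAP 3.2 defines it as "Use of rescue analgesia (amount of acetaminophen used between Baseline and Week 12". Protocol 10.4.2 has the same window: "amount of acetaminophen used between Baseline and Week 12 will be analyzed with a Wilcoxon rank-sum test".

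**Test.** SAP 8.6.2 reads: "A Wilcoxon rank-sum test will be used to compare overall pill count use over the study between saline and Ampion". The study ends at Week 24 (SAP 5.2, End of Study), so this sentence conflicts with the Week 12 window in SAP 3.2, SAP 8.6.7 and Protocol 10.4.2.

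**Place in the hierarchy.** Under SAP 8.6.7, rescue use is tested at one-sided 0.025, and only after WOMAC A, WOMAC C, PGA and the 100 mm VAS have all succeeded.

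**Treatment failures.** Protocol 10.3.11.3 and SAP 5.2 count several escalations as failure, among them "Begin opioid treatment during the study to treat worsened symptoms in the treated knee". The others are a corticosteroid increase, a clinically significant NSAID increase, an intra-articular injection of pain medicine, and knee surgery. The ITT set is all randomized patients (SAP 6.1.2), so failures stay in. SAP 8.6.4 repeats the secondary efficacy analyses in the per-protocol set without failures, and SAP 8.6.5 compares failures by Fisher's exact test as an exploratory analysis.

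**Missing counts.** SAP 7.2 covers the "number of acetaminophen pills used, missing values will be imputed when the ITT analysis population is used". The methods are multiple imputation and "single imputation methods (i.e., regression-based estimates, Baseline imputation, LOCF, and a worst/best case imputation". For the per-protocol set, SAP 6.1.3 says "No imputations will be performed".

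**First supply.** Visit 1 (Day 0) carries the step "Issue rescue medication (acetaminophen [paracetamol" (Protocol 5.1.3).

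**The concern.** The endpoint is meant to show less need for pain relief. If need outgrows acetaminophen and the patient moves to something stronger, tablet use may fall, and the rank-sum test then credits that fall. Imputation does not help, because a failure who remains under follow-up has a complete count.

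For patients who leave before Week 12, two of the listed methods do not fit a count that starts at Day 0. One has no defined input. The other, if applied to the running total, treats the unobserved weeks as tablet-free.

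Both mechanisms flatter the arm with more failures or leavers. More of them on Ampion raises the chance of a false claim; more on saline hides a true benefit.

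**Working it through.** **Figures in the documents.** There is no effect size, power, tablet distribution or failure rate for this endpoint. The stated 97% power concerns WOMAC A only. What can be used is 517 per arm, one-sided 0.025, Week 12 = Day 84, and at most one tablet every four hours (Protocol 8.3), i.e. 24/4 = 6 a day.

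**One patient.** Suppose 4 tablets a day, stopping at escalation on Day 28.
- Count with escalation: 4 × 28 = 112.
- Count without escalation: 4 × 84 = 336.

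Assume daily use is exponential with mean 1.5.
- Median 84-day total: 84 × 1.5 × ln 2 = 87.
- 112 tablets is 112/84 = 1.33 a day: 1 − exp(−1.33/1.5) = 0.59, the 59th percentile.
- 336 tablets is 4 a day: 1 − exp(−4/1.5) = 0.93, the 93rd percentile.

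Escalation improves the rank, but this patient still sits above the median.

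**Timing.** Under a second assumed model (gamma-Poisson, mean 1 a day, shape 0.7; events drawn from the upper half of need; tablets stop at the event), patients whose true need averages the 75th percentile rank as follows:

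| Event at | Mean percentile of count | Share below median |
|---|---|---|
| Week 2 | 36 | 80% |
| Week 4 | 51 | 52% |
| Week 6 | 60 | 32% |
| Week 10 | 71 | 9% |
| Uniform over 12 weeks | 55 | 40% |

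**Effect on the test.** Monte Carlo, at least 2,000 runs per scenario, 517 per arm, equal true need in both arms. Model 1: gamma shape 1, mean 1.5 a day before a cap at 6, stop day uniform from 14 to 70. Model 2: as above, event time uniform over 12 weeks. Every rate is an assumption, and every result is conditional on reaching this test.

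| Failures, Ampion v saline | False win for Ampion, model 1 | Model 2 |
|---|---|---|
| 10% v 10% | 2.2% | about 3% |
| 7% v 5% | about 4% | not run |
| 10% v 5% | 7% | 9.8% |
| 15% v 5% | 17% | 25% |
| 5% v 10% | not run | 0.5% |

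Reversing model 1 to 5% v 15% gave 16% significant in favour of saline. Using each patient's full 12-week need in model 2, i.e. an ideal imputation, returned 2% to 3% in every scenario.

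**Does excluding failures repair it?** Exclusion conditions on a post-randomization event. With heavier users failing more often (15% v 5%, no true difference), it gave 31% false success against 25% with failures kept in.

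**Imputation for leavers.** Rescue is first supplied on Day 0, so a Baseline count is either undefined or zero, and zero is the best possible score. As an outer case in model 2, setting every affected patient to zero at 10% v 5% gave 52% false success. LOCF of the running total for someone taking 4 a day who leaves on Day 28 records 112. Use per observed day is 112/28 = 4, equivalent to 336 over 84 days.

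**The case against.** **The SAP already handles leavers.** In part. Multiple imputation and a worst/best case are listed beside Baseline imputation and LOCF, so it would be wrong to infer that nothing places leavers on the unfavourable side. But no method is primary, and the SAP does not say when a partial count is missing. Rescue use is reviewed at nearly every contact, so LOCF could mean carrying forward the last interval's use, which would not freeze the total; the text does not say which is meant.

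**Failures are examined elsewhere.** True. Under model 1, Fisher's test was significant in every run at 15% v 5% and in 84% of runs at 10% v 5%, so a large imbalance would be seen. It would not alter the gated p-value.

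**Failures are not simply ranked as good low users.** Correct. A reader might infer this, but rank depends on when the change occurs and on earlier use, and late switchers stay high. Nor do the documents say that tablet use stops after escalation; the simulations assume it.

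**The error rates overstate the risk.** A reader might take 17% as the trial's type I error for this claim. It is not. It assumes Ampion fails three times as often as saline, and it applies only after Ampion has won four earlier tests.

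**Worst rank changes the endpoint.** This stands. It makes a composite that failures alone can drive: at 5% v 10% failures with equal tablet need, model 2 rejected in favour of Ampion in 7.9% of runs. That argues for a labelled sensitivity analysis, not for replacing the gated test.

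**Conclusion.** The concern holds in a limited form. The gated ITT test ranks acetaminophen alone, gives no rule for counts after treatment failure, and so credits any fall in tablets that follows escalation. Baseline imputation has no valid input for this endpoint, and LOCF is unsuitable if applied to the cumulative count. The primary imputation method and the time window are both unsettled.

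Size and direction cannot be derived from the documents. With failure rates similar in both arms, the error rate stays near nominal. With a difference of five percentage points, the illustrations give 7% to 10% instead of 2.5%. These rest on assumed tablet distributions, a complete stop in tablet use after the event, and success at all four earlier gates. As this is the last gated secondary test, the matter should be corrected but does not threaten the co-primary conclusions.

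**What to change.** Before the interim unblinding, by which time Protocol 10.3.10 requires the final SAP:

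1. **SAP 7.2.** Delete Baseline imputation and LOCF for the tablet count. Define a count as incomplete when follow-up ends before Week 12. Base the primary handling on tablets per day under observation to Week 12, or on multiple imputation of interval counts. Name one as primary and, if multiple imputation is chosen, say how the rank-sum results are combined.
2. **SAP 8.6.2, window.** Replace the whole-study window with Baseline to Week 12, to match SAP 3.2 and 8.6.7.
3. **SAP 8.6.2, sensitivity analysis.** Add an ITT analysis giving the worst rank to every patient who meets a treatment-failure criterion before Week 12. Label it rescue or escalation and report it beside the plain count, which remains the gated analysis.

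The cost is SAP wording, one derived variable and one extra analysis; treatment failures are already a planned listing (SAP 10.2). The gated test still counts acetaminophen alone, so a result on it should be read beside the sensitivity analysis.

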### 8.6.3 Subset analyses

The two co-primary endpoints and three secondary effectiveness endpoints will be analyzed by subsets for:

- (a) ages <60, [60, 70), and  $\geq 70$ ,
- (b) men and women,
- (c) white and other,
- (d) Non-Hispanic and Hispanic

### 8.6.4 Sensitivity analyses

The two co-primary endpoints and three efficacy secondary endpoints will be re-analyzed separately in the per-protocol population to exclude treatment failures.

### 8.6.5 Exploratory Endpoints

A Bayesian meta-analysis for Likert WOMAC A pain subscore including KL4 patients from studies AP-003-A, AP-003-B, AP-003-C, AP-004, and AP-013. The model is constructed for WOMAC A change from baseline for patient  $i$  in study  $j$

$$Y_{i,j} \sim N(\mu_{i,j}, \sigma^2)$$

$$\mu_{i,j} = \alpha_j + \delta_j T_i + \beta BL_i$$

$$\alpha_j \sim N(\alpha, \sigma_\alpha^2)$$

$$\delta_j \sim N(\delta, \sigma_\delta^2)$$

$$\alpha \sim N(0, 100)$$

$$\delta \sim N(0, 100)$$

$$\sigma_\alpha \sim U(0, 10)$$

$$\sigma_\delta \sim U(0, 10)$$

$$\sigma \sim U(0, 10)$$

Where  $T_i$  is the treatment assignment (0 saline or control; 1=Ampion) and  $BL_i$  is the baseline WOMAC A score.  $\alpha_j$ 's represent the control means across studies.  $\delta_j$ 's represent the treatment effects across studies.  $\sigma_\alpha$  and  $\sigma_\delta$  represent the heterogeneity of control rates and treatment effects, respectively. Sensitivity analyses will be reported that increase the priors on the variance parameters from  $U(0, 10)$  to  $U(0, 500)$ . The posterior means and 95% credible intervals will be reported for each treatment by study and treatment effect by study.

Change in WOMAC A pain sub score between Baseline and Weeks 2, 4, 6, 8, 10, and 24 will be analyzed using the MMRM model described for the primary analysis.

Change in WOMAC B stiffness sub score between Baseline and Weeks 2, 4, 6, 8, 10, 12 and 24 will be analyzed using the MMRM model described for the primary analysis.

Change in WOMAC C physical function sub score between Baseline and Weeks 2, 4, 6, 8, 10, and 24 will be analyzed using the MMRM model described for the primary analysis.

Change in PGA between Baseline and Weeks 2, 4, 6, 8, 10, and 24 will be analyzed using the MMRM model described for the primary analysis.

OMERACT-OARSI responder status, defined using Scenario D criteria, will be analyzed using separate logistic regression models for each visit.

Treatment failures will be analyzed with a Fisher's exact test.

Cumulative distribution function (CDF) plots will be used to compare WOMAC A pain and WOMAC C function endpoints for Ampion vs. saline arms.

If collected, the differences in urine analysis will be evaluated between treatment groups at Week 12.

Continuous secondary endpoints and their change from Baseline will be summarized by visit and treatment arm. Change from Baseline will include a 95% CI.

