1.5 Clinical Experience

Ampio has conducted multiple clinical studies to evaluate the treatment effect and safety of Ampion in subjects with OAK. Ampion has been administered across six clinical studies as a single IA injection or as three IA injections administered every two weeks. Four single-dose pivotal Phase 3 studies, two multi-dose studies, and one multiphase single-dose Phase 1b study have been completed. An overview of the efficacy studies is provided in the [Table 1.2](#).

For the clinical development program, all patients were required to have x-ray findings demonstrating KL 2, 3, or 4 disease severity. All studies enrolled patients with KL 4 disease. In addition, eligible subjects had at least moderate pain at Baseline (defined as a score of at least 1.5 on the WOMAC Index 3.1, as measured by the 5-point Likert pain subscale at screening) in the study knee, which was to have been symptomatic for greater than six months with a clinical diagnosis of OA confirmed by radiological evidence. The clinical effects of treatment on OA pain were evaluated during clinic visits, with phone call follow-ups according to the study visit schedule.

Table 1.2 Summary of the Studies Conducted with Ampion Administered as an Intra Articular Injection to the Knee

Study	Phase	N	N: KL 2, 3, 4	Route	Primary outcome	Primary endpoint	Additional outcomes	Test product
Single-Injection Phase 3 Studies in Support of Efficacy & Safety								
AP-003-A	3	329	115 / 139 / 75	Single IA injection	WOMAC A pain, 5- point Likert scale	Week 12	WOMAC B WOMAC C PGA OMERACT -OARSI Rescue analgesia	Ampion, 4 mL and 10mL
AP-004	3	538	133 / 195/ 210	Single IA injection	WOMAC A pain, 5- point Likert scale	Week 12	WOMAC C PGA WOMAC A pain over 12 weeks	Ampion, 4 mL

Study	Phase	N	N: KL 2, 3, 4	Route	Primary outcome	Primary endpoint	Additional outcomes	Test product
AP-003-C	3	168	0 / 0 / 168	Single IA injection	OMERACT- OARSI responder	Week 12	WOMAC A, B, C and PGA	Ampion, 4 mL
AP-003-B	3	480	101 / 247 / 132	Single IA injection	WOMAC A pain, 5- point Likert scale	Week 12	WOMAC B WOMAC C PGA Rescue analgesia WOMAC A pain with movement, pain at rest	Ampion, 4 mL
Additional Clinical Studies in Support of Safety								
AP-007	1 / 2	47	2 / 23 / 15	Multiple IA injection; 3 injections, every 2 weeks	WOMAC A pain, 5- point Likert scale	Week 20	WOMAC B WOMAC C PGA Physical activity Radiologic changes	Ampion, 4 mL

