10.3.6 Definition of Study Visits

This clinical trial has a total of 11 study visits, including telephone contacts, during the 24-week study (see Table 6.1). The time-on-study for each patient observation will be defined relative to Day 0, the day of the initial dose. For analysis, the Baseline measure is the latest measure prior to initiation of treatment. For analysis of Baseline WOMAC A pain, the Baseline pain score is the average of all scores measured during days -6 to 0, prior to injection of treatment. For analysis of Week 12 WOMAC A pain, the Week 12 pain score is the average of all scores measured during the seven days prior to and including the Week 12 office visit.

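### The exploratory Bayesian meta-analysis gives all five studies one residual variance, although AP-013's pain score is an average of up to seven daily scores and the earlier studies are described as visit-based

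*SAP*

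**What the plan says.** SAP 8.6.5 describes "A Bayesian meta-analysis for Likert WOMAC A pain subscore including KL4 patients from studies AP-003-A, AP-003-B, AP-003-C, AP-004, and AP-013". The outcome line reads, up to its closing bracket, "Y_{i,j} \sim N(\mu_{i,j}, \sigma^2", and the mean is "\mu_{i,j} = \alpha_j + \delta_j T_i + \beta BL_i". The intercept and the treatment effect carry a study index. The residual variance and the baseline slope do not, and no prior is listed for the slope. The planned check on the model is limited to the priors: "Sensitivity analyses will be reported that increase the priors on the variance parameters from" U(0, 10) to U(0, 500). Study-level precision is an output: "The posterior means and 95% credible intervals will be reported for each treatment by study and treatment effect by study". The section names no time point and does not say which AP-013 pain score enters.

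For AP-013, Protocol 10.3.6 says that "the Baseline pain score is the average of all scores measured during days -6 to 0", before injection, and that "the Week 12 pain score is the average of all scores measured during the seven days prior to and including" the Week 12 office visit. SAP 3.1 uses the same weekly score for the primary endpoint. For the earlier programme, Protocol 1.5 says: "The clinical effects of treatment on OA pain were evaluated during clinic visits, with phone call follow-ups according to the study visit schedule". It mentions no diary.

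**The concern.** A mean of several daily readings carries less day-to-day noise than one reading, unless that noise is absent or perfectly correlated within the week. If AP-013 enters as a diary average and the earlier studies enter as single readings, the five studies should not be expected to share a residual SD.

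A common sigma is a compromise weighted by study size. AP-013 is the largest study, so the compromise falls nearer its value. The earlier studies would then look more precise than they are and pull somewhat too hard on the pooled effect, while AP-013 would look less precise than it is. The quantities at stake are the study-level credible intervals and, through the weights, the pooled effect and the estimated heterogeneity between studies. Widening the variance priors does not test this, because sigma stays common under either prior.

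**Working it through.** **The plan's own figures.** Protocol 4.1 and SAP 2.4 give pain changes of -0.83 and -0.62 (difference 0.21), SD 0.85 and one-sided alpha 0.025.

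- Sample size per arm for 90% power: 2 × (1.960 + 1.282)² × 0.85² / 0.21² = 344.3, so 345 per arm and 690 in total, as stated.
- Power is 97.8% with 517 per arm and 97.2% with 492 per arm (984 evaluable), against the stated 97%.

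The figures reproduce. The 0.85 is the only pain SD in the documents. None is given by study or for a diary average.

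**Patients in the model.** KL 4 counts from Protocol Table 1.2 are AP-003-A 75, AP-004 210, AP-003-C 168 and AP-003-B 132, a total of 585. AP-013 adds 1,034, so it supplies 1,034 / 1,619 = 64%. At the maximum size it supplies 1,552 / 2,137 = 73%.

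**Assumptions.**
- The residual SD in each earlier study is 0.85. The ratios before shrinkage do not depend on this value.
- f is the share of single-reading residual variance that is day-to-day noise.
- rho is the correlation of that noise within the week.
- Seven daily scores are available.
- Allocation is 1:1 in every study. Table 1.3 (475 Ampion and 361 saline KL 4 patients over the whole programme) shows that this is not exact.
- All 75 AP-003-A patients count, although that study used two volumes.
- There is no dropout.

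**Formulas.**
- AP-013 SD = 0.85 × √[1 − f(1 − (1 + 6rho)/7)]
- Common sigma² = (585 × 0.85² + 1,034 × AP-013 SD²) / 1,619
- Width ratio before shrinkage = common sigma / study's own SD

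Example with f = 0.25 and rho = 0: AP-013's variance factor is 1 − 0.25 × 6/7 = 0.786, so its SD is 0.753. The common factor is (585 + 1,034 × 0.786) / 1,619 = 0.863, so the common SD is 0.790. The ratios are 0.790/0.850 = 0.929 and 0.790/0.753 = 1.048, taken before rounding.

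**After shrinkage.** I took study-level standard errors of 2 × SD / √n in a normal hierarchy with the SAP's priors on delta and sigma_delta. I compared interval widths under the common and the study-specific SDs. Two assumed sets of observed effects were used: all equal to -0.21; and -0.45, -0.10, -0.35, -0.20, -0.15 for AP-003-A, AP-004, AP-003-C, AP-003-B and AP-013.

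| f | rho | Earlier, before | AP-013, before | Earlier, after | AP-013, after |
|---|---|---|---|---|---|
| 0 | 0 | 1.00 | 1.00 | 1.00 | 1.00 |
| 0.10 | 0 | 0.972 | 1.017 | 0.975–0.988 | 1.008–1.015 |
| 0.25 | 0 | 0.929 | 1.048 | 0.937–0.969 | 1.025–1.043 |
| 0.50 | 0 | 0.852 | 1.127 | 0.868–0.936 | 1.076–1.119 |
| 0.25 | 0.5 | 0.965 | 1.021 | 0.969–0.985 | 1.011–1.019 |
| 0.50 | 0.5 | 0.929 | 1.048 | 0.937–0.969 | 1.025–1.043 |

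For f from 0.10 to 0.50 with rho = 0, nominal 95% coverage before shrinkage, 2Φ(1.96 × ratio) − 1, falls from 94.3% to 90.5% for the earlier studies and rises from 95.4% to 97.3% for AP-013. With 1,552 patients, f = 0.50 and rho = 0, the ratios before shrinkage are 0.830 and 1.098.

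**Common slope.** A simulated example gave baseline slopes of -0.55 for single readings and -0.43 for seven-day averages. Forcing one slope changed each residual SD by less than 0.003. A rough check agrees. The common slope misses the earlier studies' slope by about 0.12 × 1,034/1,619 = 0.077. With an assumed baseline variance of 0.5, this adds 0.077² × 0.5 ≈ 0.003 to the variance, or 0.003 / (2 × 0.85) ≈ 0.002 to the SD.

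**The case against.** The strongest reply is that neither premise is settled. SAP 8.6.5 does not say that diary averages enter the meta-analysis. SAP 5.2 sets the default baseline at Visit 1 unless otherwise defined, and the SAP says weekly elsewhere when it means the diary score. Protocol 1.5 is one summary sentence, and Protocol 5 and 6.1.1 describe AP-013 in similar terms of clinic visits and phone contacts although AP-013 has a diary. That sentence therefore cannot show that the earlier studies had none. No SD by study is available, and other differences between studies could offset or reverse the gap. A common residual variance is also an ordinary simplification.

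Most of this stands, and it makes the conclusion conditional. It does not remove the point. Protocol 10.3.6 is the explicit rule for analysing WOMAC A, so the diary average is the natural reading. If it is not the intended one, SAP 8.6.5 leaves two programmers free to use different data.

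Three stronger readings are tempting. A reader might infer that the intervals are certain to be wrong. The documents do not support this, because the error vanishes when day-to-day noise is nil. A reader might also blame the common baseline slope, but it hardly moves the widths. Finally, a reader might take the analysis to be the plan's test of consistent KL 4 effects. The documents list it only as exploratory and give it no decision rule.

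**Conclusion.** The point holds as a low-severity improvement. The plan's own change of scoring makes the equal-variance assumption doubtful, and no planned sensitivity analysis examines it.

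If averaging lowers AP-013's residual SD, then over the noise shares examined the earlier studies' intervals are about 1% to 13% too narrow and AP-013's about 1% to 12% too wide after shrinkage, at 1,034 patients. Correlated daily noise puts the error lower in that range. These sizes rest wholly on the assumed f and rho, on single readings in the earlier studies, and on the diary average entering for AP-013.

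The meta-analysis lies outside the testing hierarchy in SAP 8.6.7, so the co-primary and secondary conclusions are unaffected.

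**What to change.** In SAP 8.6.5:

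1. State that the change from Baseline to Week 12 is analysed, and which AP-013 score enters at each time point.
2. Replace the common sigma with study-specific values: Y_ij ~ N(mu_ij, sigma_j²), with each sigma_j given the stated U(0, 10) prior. Study-specific slopes beta_j are optional and matter little for the widths. The slope needs a stated prior in either case.
3. Add a sensitivity run that uses AP-013's visit-day Baseline and Week 12 Likert readings. Where the reading was taken at home, which the footnotes to Protocol Table 6.1 allow, use the last daily score.

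The cost is SAP wording and a few more parameters, with no new data. The downside is a less precise variance estimate for the smallest study (75 KL 4 patients). The change should be made before unblinding, since SAP 8.6.6 would otherwise class it as post hoc.
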